3.3.4.1.2 Exclusion Criteria

Married females or those with chronic diseases or those already taking iron and/or prebiotic supplements will be excluded from the study.

3.3.5. Sampling

3.3.5.1 Sampling Technique

The technique of convenience sampling will be used for the current study.

3.3.5.2 Sample Size

Each group will consist of 15 study subjects for the purpose of convenience and the total sample size will be 75.

3.3.6 Treatment Plan

For this phase of the study, 4 best treatment combinations of pre-biotics and iron fortificants will be chosen based on the results of animal trials while one group will be taken as control (Table 1).

Table 1: Treatment Plan for Anemic Women

GROUP	DIET PLAN
D ₀	Control Group (Placebo)
D ₁	Best Treatment Combination 1
D ₂	Best Treatment Combination 2
D ₃	Best Treatment Combination 3
D ₄	Best Treatment Combination 4

Study participants will be randomly chosen to receive either the best treatment combination 1, 2, 3, 4 or the placebo for 12 weeks on daily basis.

3.3.7 Efficacy Trials

Up to three months, blood samples will be collected from overnight fasted women on monthly basis.

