Project Title: Probing the Synergistic Effect of Pre-biotics & Iron Fortificants in Anemic Subjects	
Principal Investigator: [name]	
NCT No.: NCT03894449	
Date: January 11, 2019	
IRC Ref No. :	Organization: UVAS, Lahore
Address: UVAS, [name]	[contact]
Other Investigators: [name]	Organization: UVAS, Lahore
Address: UVAS, [name]	[contact]

MATERIALS AND METHODS

The study will consist of determining the synergistic effect of pre-biotics and iron fortificants in anemic human subjects.

Study Design

A double blind, randomized controlled trial will be used for the purpose of this study.

Study Site

The study will be conducted in Islamabad and/or Lahore, depending on the availability of the required sample size with the desired profiles.

Study Duration

The trial will last for 3 months.

Study Population

The study population will comprise of university going iron deficient female adults (age 18-25 years).

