3.3.7.6 Statistical Analysis

In order to determine the level of significance, the statistical analysis of the obtained data will be done for the purpose of which, SPSS version 23.0 will be used. CRD will be used during the experiment and differences will be considered significant at P - value < 0.05 (Steel and Torrie 1980).

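### Blood is taken monthly but the only named analysis is a CRD, with no rule on sampling after stopping, analysis set or missing values, so a completers-only final comparison is likely

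*Combined protocol and SAP*

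**What the plan says.** - **Design (Study Design).** "A double blind, randomized controlled trial will be used for the purpose of this study".
- **Size (3.3.5.2).** "Each group will consist of 15 study subjects for the purpose of convenience and the total sample size will be 75".
- **Treatment (3.3.6).** Women are randomised to "the best treatment combination 1, 2, 3, 4 or the placebo for 12 weeks on daily basis".
- **Sampling (3.3.7).** "Up to three months, blood samples will be collected from overnight fasted women on monthly basis". This matches Study Duration: "The trial will last for 3 months". No baseline sample is named.
- **Analysis (3.3.7.6).** Apart from the software, the content is one sentence: "CRD will be used during the experiment and differences will be considered significant at P - value < 0.05".

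Section 3.3.7.1 sends the samples collected from all groups for haematology. That covers samples that exist, not women who were randomised. No section says what happens to sampling when a woman stops the product, which women form the analysis set, which visit is primary, or how a missing value is treated. There is no allowance for dropout.

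**The concern.** I read CRD as completely randomised design. Its ordinary analysis is a one-way comparison with one value per subject, whereas this trial will produce up to three monthly values per woman. An analyst who applies the named method at the natural point, the end of the 12 weeks, has to pick the last value. A woman without it then contributes nothing, even if her month-1 and month-2 values are on file.

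Randomisation protects a comparison only if the randomised women are the ones compared. If more women leave one arm than another, and those who leave were doing worse or better than those who stay, the combination-versus-placebo difference is distorted. The direction depends on which arm loses whom. With arms of 15, three losses are 3/15 = 20%, so a handful of women is enough. Samples not taken after a woman stops cannot be recovered later.

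**Working it through.** **1. The plan's own figure.** 5 arms × 15 = 75, as stated. The documents give no power, SD, effect size, correlation or dropout rate, so everything below in SD units rests on assumed inputs.

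**2. What the named method uses.** There are three monthly values per woman. A one-way comparison at the final visit uses one of them. A woman who leaves after month 2 has two values, and neither enters.

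**3. Size of the completers' bias, by algebra.** In one arm, let *p* be the share lost and *g* the mean final outcome of completers minus that of women lost. The completers' mean exceeds the mean of all randomised women by *p × g*. For the difference between two arms with the same *g*:

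bias = (p_active − p_placebo) × g

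Assume *g* between 0.5 and 1.0 SD:

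| Loss, active / placebo | Calculation | Bias (SD) |
|---|---|---|
| 20% / 5% | 0.15 × 0.5 to 0.15 × 1.0 | +0.075 to +0.15 |
| 5% / 20% | −0.15 × 0.5 to −0.15 × 1.0 | −0.075 to −0.15 |
| 20% / 20% | 0 × g | 0 |
| any, g = 0 | – | 0 |

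**4. The same by simulation.** Assumptions: 15 per arm, correlation 0.7 between visits, true final difference 0.80 SD, and women with worse last values more likely to stop. The strength of that dependence was varied (log-odds slope 0.5 to 1.5 per SD in the main set).

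| Loss, active / placebo | Completers' difference (SD) | Repeated-measures model (SD) |
|---|---|---|
| 20% / 5% | 0.86 to 0.93 | about 0.80 |
| 5% / 20% | 0.67 to 0.74 | about 0.80 |
| 20% / 20% | about 0.80 | about 0.80 |

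The error is roughly 0.06 to 0.14 SD in either direction, in line with step 3. The larger values need strong dependence of stopping on outcome.

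**5. Precision.** At 20% / 5% loss the expected numbers are 15 × 0.80 = 12 and 15 × 0.95 = 14.25.

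- Completers, unadjusted: SE = √(1/12 + 1/14.25) = 0.39 SD.
- Adjusted for a baseline correlated 0.7 with the final value: 0.392 × √(1 − 0.7²) = 0.392 × 0.714 = 0.28 SD.

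Simulated standard errors agree: about 0.37 to 0.40 for completers and 0.28 to 0.29 for the baseline-adjusted repeated-measures model, including under equal loss. A repeated-measures model without the larger gain from baseline adjustment moved the SE only from 0.40 to 0.38. So most of the precision gain comes from the baseline value. The intermediate months mainly serve to remove the bias.

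**The case against.** A reader might infer more than the text supports, and the strongest objection is aimed at that.

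- **That the sampling sentence ends sampling when a woman stops.** It does not. It gives the length of the schedule, which equals the trial length and the treatment period. No section stops sampling at discontinuation.
- **That the plan prescribes a completers' analysis at month 3.** It does not. No section names month 3 as the endpoint, discards earlier values or removes a woman from her group. CRD describes a layout and contains no exclusion rule.

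Both points stand, and the concern is therefore limited to an omission and its likely consequence.

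The figures can also be challenged. If women stop for reasons unrelated to outcome, such as tolerability alone, there is no bias. A shift of 0.13 SD is only a third of the completers' SE (0.13/0.39), in a trial where 15 per arm detects about 1.06 SD pairwise with 80% power even without loss. The simulated advantage of the repeated-measures model is partly built in, because loss was made to depend on observed values, the condition under which such a model is unbiased. All of this is fair. It is why the numbers are illustrative and why a sensitivity analysis belongs in the fix.

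Finally, an as-randomised analysis set and any stated missing-data rule would close the gap formally. That is true, but the repeated-measures model uses data already scheduled and is materially more precise here, so it is more than a matter of taste.

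**Conclusion.** The concern holds in a limited form. The plan takes repeated samples but names only a one-value-per-woman layout, and is silent on sampling after stopping, the analysis set and missing values. A completers-only comparison at the end of treatment is neither prescribed nor excluded. It is what the named method would ordinarily produce.

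The size cannot be derived from the documents. Under the assumptions in the working, unequal outcome-related loss of 20% and 5% moves a true 0.80 SD difference by roughly 0.06 to 0.14 SD, up or down. Equal loss with the same pattern in both arms, or loss unrelated to outcome, gives none. The gain in precision from about 0.39 to 0.28 SD depends on the assumed correlation of 0.7 with baseline, but not on loss being unequal. This should be settled before enrolment; it does not invalidate the design.

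**What to change.** **In 3.3.7, add:** a baseline sample is taken before the product is started. Every randomised woman is asked for all scheduled monthly samples to the end of the 12-week period, whether or not she is still taking the product. The date and reason for stopping are recorded. The existing wording on the three-month schedule can stay.

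**In 3.3.7.6, add:** women are analysed in the arm to which they were randomised. The analysis is a mixed model for repeated measures on all monthly values, with terms for arm, month, arm-by-month and baseline, and the arm difference at the final visit is read from it. A simple sensitivity analysis covers loss that depends on unobserved values, for example by shifting the unobserved final values in one arm over a stated range.

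**Cost.** Some wording, a baseline draw if none is already intended, and follow-up draws at visits already scheduled. SPSS 23.0 can fit the model. One small downside: values taken after stopping move the estimate towards the effect of being assigned to the product rather than of taking it, and the text should say that this is the intended question.

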3.3.7.1 Hematological Analysis

The collected blood samples from all the groups will be subjected to hematological analysis. Blood complete picture including RBC indices such as Haemoglobin (Hb) levels and Hematocrit (Hr) levels & Leukocytes including Lymphocytes, Monocytes, Neutrophils and Basophils etc will be evaluated as per their respective protocols (Al Haj et al. 2011).

3.3.7.2 Iron Biomarkers

Blood serum biomarkers will be determined on the basis of analysis of obtained sera.

3.3.7.2.1 Serum Folate

Serum folate of the samples will be measured using the method mentioned by Shuaibi et al (Shuaibi et al. 2008).

3.3.7.2.2 Serum Iron

Concentration of serum iron concentration will be measured using Atomic Absorption Spectrophotometer (Wojciak et al. 2013).

3.3.7.2.3 Serum Ferritin

Ciba-Corning's Automated Chemiluminescence System's (ACS 180) commercially available kit will be employed to determine the levels of serum ferritin (Kazuaki et al. 2011).

3.3.7.2.4 Serum Transferrin

It will be measured as per the procedure mentioned by Al-Buhairan and Oluboyede (Al-Buhairan and Oluboyede 2000).

3.3.7.2.5 Total Iron Binding Capacity (TIBC)

The standard formula for the determination of TIBC will be used;

$$\text{TIBC} = \text{Transferrin} \times 24$$

3.3.7.2.6 Transferrin Saturation Fraction (TRSF)

TrSF will be calculated as per the following expression;

$$\text{TrSF} = \frac{\text{Serum Iron Concentration}}{\text{Total Iron Binding Capacity}} \times 100$$

3.3.7.3 Liver Function Tests (LFTs)

LFTs including AST (Aspartate Aminotransferase), ALT (Alanine Aminotransferase), ALP (Alkaline Phosphatase) and Total Bilirubin will be conducted (Basuny et al. 2009).

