3.3.7.4 Renal Function Tests (RFTs)

RFTs including blood urea by GLDH-method and creatinine by Jaffe-method will be measured using their respective commercial kits (Jacobs 1996; Thomas 1998).

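### Testing liver and renal results only at P < 0.05 can miss one or two women with gross elevations in an arm of 15; add counts above the reference limit and individual listings

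*Combined protocol and SAP*

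**What the plan says.** Section 3.3.7.3 states that "LFTs including AST (Aspartate Aminotransferase), ALT (Alanine Aminotransferase), ALP (Alkaline Phosphatase) and Total Bilirubin will be conducted". Section 3.3.7.4 states that "RFTs including blood urea by GLDH-method and creatinine by Jaffe-method will be measured using their respective commercial kits". That makes six analytes. Neither section gives a reference limit, a count of abnormal values or a review of individual results.

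Section 3.3.7.6 is the only analysis text. It says that "CRD will be used during the experiment" and that "differences will be considered significant at P - value < 0.05". CRD is read here as a completely randomised design. No test is named, and no separate treatment is given to any outcome.

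On size, 3.3.5.2 says: "Each group will consist of 15 study subjects for the purpose of convenience and the total sample size will be 75". Section 3.3.6 has four combination arms and one placebo arm. On timing, 3.3.7 says that "blood samples will be collected from overnight fasted women on monthly basis", for up to three months; it does not mention a sample before the first dose.

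**The concern.** A rule based on differences between arms asks whether a whole arm has moved. Liver and renal tests can also be abnormal in one or two people while the rest of the arm is unaffected, and an arm of 15 has little room to show that through its mean. The affected woman raises the arm mean, but she also raises the error variance by which the difference is judged.

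A report that follows 3.3.7.6 and nothing more could therefore say that liver and renal function did not differ significantly, with a gross elevation in one woman left invisible. The measurements that would reveal it are already planned. What is missing is any way of reporting them other than a between-arm P value.

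**Working it through.** **Inputs from the documents.** Five arms (3.3.6), 15 women per arm (3.3.5.2), significance level 0.05 (3.3.7.6). The stated total reproduces: 5 × 15 = 75. No power, SD or effect size is stated, so there is no power figure to reproduce.

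**Assumptions.** Two-sided testing; a one-way comparison of arm means; one analyte at one visit. In the limit, m women in one arm share a value k so large that everyone else's variation is negligible.

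**One-way F (4 and 70 df).**
- Between arms: MSB = m²k²(1/15 − 1/75)/4 = m²k²/75.
- Within arms: MSW = k² × m(15 − m)/15 ÷ 70.
- The k² cancels, so F = 14m/(15 − m).
- m = 1: 14/14 = 1.00, P = 0.41.
- m = 2: 28/13 = 2.15, P = 0.083.
- m = 3: 42/12 = 3.50, P = 0.012.
- Critical value: 2.50. Three affected women are needed.

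**Unadjusted contrast with placebo on the pooled error (70 df).** t = (mk/15)/√(2·MSW/15) = √(35m/(15 − m)).
- m = 1: √2.50 = 1.58, P = 0.12.
- m = 2: √5.385 = 2.32, P = 0.023.
- Critical value: 1.99. This test can flag two women but not one.

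**Two-sample t using only the two arms (28 df).** t = √(14m/(15 − m)).
- m = 1: 1.00, P = 0.33.
- m = 2: 1.47, P = 0.15.
- Critical value: 2.05. Four affected women are needed.

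**Finite shifts.** These are 20,000 simulated trials per setting, with unit-SD normal values and assumed shifts of 3 to 50 SD. The contrast and the t test were counted only when they flagged a rise.

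| Test | One woman flagged | Two women flagged |
|---|---|---|
| One-way F | 0–5% | 4–19% |
| Two-sample t | 0–4% | 0–9% |
| Unadjusted pooled-error contrast | 1–12% | 14% (3 SD), 25% (5 SD), 47% (10 SD), 65% (15 SD), 76% (20 SD) |

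With nobody affected, F rejects in 4.9% of trials, so its rate for one affected woman is no better than its false-positive rate. Log-normal values gave nearly the same results. Rank tests at a 15 SD shift flagged 4–7%, and log-scale tests at 3- to 10-fold rises flagged 4–13%, for one or two women.

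**What counts can and cannot do.** A P value on counts is no cure: by Fisher's exact test, 2/15 against 0/15 gives P = 0.48, and 5/15 against 0/15 is needed for P = 0.042. The gain comes from showing the count, its interval and the values. With no abnormal values, the exact two-sided 95% upper limit is 1 − 0.025^(1/15) = 21.8% for one arm and 1 − 0.025^(1/60) = 6.0% for the four combinations pooled (4 × 15 = 60).

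**The case against.** Several objections have force.

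- **No test is named.** Correct: the comparison of means is inferred from the design and the word differences. Rank and log-scale versions lead to the same conclusion, so the point does not depend on that reading alone.
- **Severity can matter.** A reader might infer that no test would ever respond, however extreme the values. That is too strong. With two affected women, the unadjusted pooled-error contrast becomes significant at very large shifts. The statement holds for one woman under every test tried, and for two women only in the limit of F and the two-sample t.
- **The heading.** A reader might infer from "3.3.7 Efficacy Trials" that these tests are classed as efficacy endpoints. The same heading also holds the statistics and ethics subsections, so its numbering carries no analytic meaning.
- **No safety claim is made.** A reader might infer that the trial would reach a wrong safety conclusion. The plan states no safety objective or conclusion, and does not say that non-significance means safety. Nor does it label these as its only safety measurements; the blood count in 3.3.7.1 could serve that purpose too. What stands is narrower: no other reading of these results is provided.
- **More analytes and visits give more chances.** True, but six independent tests at 0.05 give 1 − 0.95⁶ = 26% for at least one false positive. Most such signals would not identify the affected woman.

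**Conclusion.** The point holds as a cheap improvement to the analysis text, not as an error in the plan. Under the natural reading of 3.3.7.6, the stated rule cannot be relied on to show one grossly affected woman in an arm of 15, and it mostly misses two. The exception is the unadjusted pooled-error contrast with two women, which flags about half of trials at 10 SD and more beyond that.

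The limiting F and t values rest only on the stated arm sizes and the assumed test. The detection percentages also rest on assumed distributions and shift sizes, because the documents give no SDs. That harm would take the form of isolated elevations is a possibility to be covered; the documents say nothing either way.

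**What to change.** In 3.3.7.6, state that for AST, ALT, ALP, total bilirubin, urea and creatinine a non-significant difference will not be taken as evidence of no harm. For each test, report by arm and for all four combinations pooled:

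- the number and percentage of women with any on-treatment value above the laboratory's upper reference limit, with exact 95% confidence intervals;
- a listing of the individual values.

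Add shift tables only if a pre-dose sample is taken, which 3.3.7 does not state.

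The cost is a sentence and a few tables from measurements already planned. The downside is that some unaffected women will exceed the limit by chance. If 2.5% of unaffected values lie above it, with three independent visits, that is 1 − 0.975³ = 7.3% of women per test and 1 − 0.975¹⁸ = 36.6% on at least one of six independent tests. These rates are assumptions. The listings must therefore show how large each value is.

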3.3.7.4 Renal Function Tests (RFTs)

RFTs including blood urea by GLDH-method and creatinine by Jaffe-method will be measured using their respective commercial kits (Jacobs 1996; Thomas 1998).

3.3.7.5 Immunoglobulins

Total Immunoglobulins will be determined using the technique of ELISA (Enzyme linked Immunosorbent Assay).

3.3.7.6 Statistical Analysis

In order to determine the level of significance, the statistical analysis of the obtained data will be done for the purpose of which, SPSS version 23.0 will be used. CRD will be used during the experiment and differences will be considered significant at P - value < 0.05 (Steel and Torrie 1980).

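### The analysis section calls any difference significant at P < 0.05 without naming a primary endpoint, deciding visit, set of arm comparisons or multiplicity control

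*Combined protocol and SAP*

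**What the plan says.** Section 3.3.7.6 names the software, a completely randomized design (CRD) and a threshold: "CRD will be used during the experiment and differences will be considered significant at P - value < 0.05". It cites a statistical reference but names no test, model, contrast or post-hoc procedure.

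The other sections show how much this rule has to cover:

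- **Arms.** Section 3.3.6 randomizes women to "the best treatment combination 1, 2, 3, 4 or the placebo for 12 weeks on daily basis", which makes five groups.
- **Visits.** Section 3.3.7: "Up to three months, blood samples will be collected from overnight fasted women on monthly basis". It does not say whether a baseline sample is taken.
- **Measures.** Sections 3.3.7.1 to 3.3.7.5 list haematology, iron markers, liver tests, renal tests and immunoglobulins. All sit under the Efficacy Trials heading and none is ranked above another. The haematology list is open-ended: "Leukocytes including Lymphocytes, Monocytes, Neutrophils and Basophils etc will be evaluated".
- **Sample size.** Section 3.3.5.2: "Each group will consist of 15 study subjects for the purpose of convenience and the total sample size will be 75". No endpoint, effect size, SD or power is given.

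**The concern.** A 5% threshold limits error for one test. Here it applies to any difference, on any measure, at any monthly visit, between any arms. The plan does not say whether an overall F-test comes first or which pairwise tests follow. A power calculation often shows which endpoint was intended, but there is none here.

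Two things are at stake. First, ineffective combinations could be declared effective well above 5% of the time. Second, a reader could not tell a planned result from one picked after the data were seen, because the trial has no defined success criterion.

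**Working it through.** **The plan's own figure.** 5 groups × 15 = 75, as stated. It has no power basis to reproduce.

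**Count of measures.**

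- Haematology 6: Hb, haematocrit, lymphocytes, monocytes, neutrophils, basophils.
- Iron panel 6: folate, iron, ferritin, transferrin, TIBC, transferrin saturation (TrSF).
- Liver 4, renal 2, immunoglobulin 1.
- Total 6 + 6 + 4 + 2 + 1 = 19.

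Section 3.3.7.2.5 defines TIBC as transferrin × 24. A test on TIBC therefore gives the same result as one on transferrin, which leaves 18 distinct measures. For a narrower count I take seven as efficacy measures: Hb, haematocrit, folate, iron, ferritin, transferrin and TrSF. That split is mine; the protocol makes none.

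**Set-up.** Five arms of 15, so pooled df = 75 − 5 = 70. Two-sided tests are assumed because sidedness is not stated. Critical values at 0.05 are |t| = 1.994 and F(4, 70) = 2.503.

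**One measure, one visit, no true effect.**

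- Omnibus F: 5.0%.
- A placebo comparison significant after a significant F: 4.0%.
- Any of four unadjusted placebo comparisons: 15.4%. This is 1 − P(all four |t| ≤ 1.994), integrated over the shared placebo mean and pooled SD.

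**Several measures and visits.** Simulation under no true effect. Assumptions: three post-baseline visits, and exchangeable (measure, visit) correlations of (0.3, 0.6), (0.5, 0.8) and (0.7, 0.8). The ranges span these three settings.

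| Chance of at least one false positive | (a) Omnibus F | (b) Placebo comparison after significant F | (c) Unadjusted placebo comparisons |
|---|---|---|---|
| 7 measures, final visit | 19–28% | 16–23% | 47–64% |
| 7 measures, 3 visits | 34–56% | 30–50% | 71–92% |
| 18 measures, 3 visits | 51–84% | 47–78% | 87–99.7% |

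Expected false positives on reading (c):

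- 7 × 4 × 3 = 84 tests, and 84 × 0.05 = 4.2.
- 18 × 4 × 3 = 216 tests, and 216 × 0.05 = 10.8.

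**Cost of control.** Dunnett's two-sided critical value for four comparisons at 70 df is 2.499. The detectable difference d (in SD) at 80% power solves P(T > c) = 0.80, where T is noncentral t with 70 df and noncentrality d × √(15/2). With c = 1.994, d = 1.037. With c = 2.499, d = 1.223. Neither is adjusted for baseline.

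**The case against.** The omission itself is not in dispute; the objections concern its size and the remedy.

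- **CRD points to one-way ANOVA, so reading (c) is the least supported by the text.** This is fair. Column (c) is best read as the worst case, and (a) and (b) as the main figures. An F-test covers the arms for one measure at one visit; it does nothing across measures or visits.
- **One repeated-measures group test per measure is also a natural reading.** With seven measures this gives 18–28% for some significant group F and 16–23% for an F-gated placebo comparison. That is about half the three-visit figures and still well above 5%.
- **The correlations are assumed and could be higher.** At 0.9 between measures and 0.9 between visits, the F-based readings for seven measures give about 10–20%. The table's ranges are therefore not bounds, but the direction does not change.
- **Liver and renal tests may be safety monitoring.** They may be, but the protocol does not say so. The seven-measure rows leave them out.
- **With one measure and visit named, an F-gate already holds 5%, so Dunnett adds nothing.** This is true only when no combination works. If one works strongly, the F-test is passed almost automatically and the other three placebo comparisons are unadjusted. Integrating as above with three comparisons instead of four, their joint error is then about 12.5%.
- **Comparing combinations with placebo does not test synergy.** That is correct, but it is a separate issue from error control.
- **The cited reference may fix a comparison procedure.** It cannot be checked here, and it could not supply this trial's endpoint or visit.

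**Conclusion.** The concern holds and must be fixed before data are seen. That no endpoint, visit, comparison set or error control is named follows from the text and needs no assumption. The error rates assume no true effect, two-sided tests, three post-baseline visits and the stated correlations.

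On the F-based readings, seven measures give 16–28% at the final visit and 30–56% over three visits. Unadjusted placebo comparisons give 47–92%. Even with correlations of 0.9, the F-based rates stay at about twice the nominal 5% or more. Following the plan as written would therefore give unreliable efficacy claims.

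**What to change.** In section 3.3.7.6:

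1. Name one primary endpoint and time point. Haemoglobin at week 12 is one example; an iron marker is also arguable, and the choice is the sponsor's.
2. Compare the four combinations with placebo by Dunnett's test at two-sided familywise 0.05 (critical value about 2.50 at 70 df). Other valid familywise procedures exist, but one must be named.
3. Label all other measures, earlier visits and combination-versus-combination contrasts as secondary or exploratory. Report them as estimates with 95% confidence intervals and no confirmatory claims.
4. State that TIBC is derived from transferrin and is not tested separately.

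The cost is one paragraph of text, with no extra subjects, visits or assays. The detectable difference per placebo comparison at 80% power rises from about 1.04 SD (unadjusted) to 1.22 SD, and the other measures can no longer support confirmatory claims.

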3.3.4.1 Inclusion and Exclusion Criteria

3.3.4.1.1 Inclusion Criteria

All willing anemic female adults without any chronic diseases such as diabetes or hypertension will be included in the study.

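### The analysis section names only a completely randomised design, whose standard analysis ignores baseline; a pre-specified month 3 ANCOVA on the pre-dose value may add precision with 15 women per arm, if a pre-dose sample exists

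*Combined protocol and SAP*

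**What the plan says.** The analysis plan is section 3.3.7.6 alone. It names SPSS 23.0 and states that "CRD will be used during the experiment and differences will be considered significant at P - value < 0.05". No section names an analysis model, an analysis visit, a covariate, a change score or a repeated-measures method.

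The design is five arms: section 3.3.6 sets four treatment arms, to be selected from animal results, against one control, with treatment or "the placebo for 12 weeks on daily basis". Section 3.3.5.2 says "Each group will consist of 15 study subjects for the purpose of convenience" and that "the total sample size will be 75". It gives no power, SD or target difference.

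On sampling, section 3.3.7 says "Up to three months, blood samples will be collected from overnight fasted women on monthly basis". It does not say whether one of these samples precedes the first dose. The Study Population paragraph ("The study population will comprise of university going iron deficient female adults") and section 3.3.4.1.1 ("All willing anemic female adults without any chronic diseases") imply some assessment before treatment. They do not show that the outcomes in 3.3.7.1 to 3.3.7.5 are all measured then.

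**The concern.** The usual one-way analysis of a CRD has a treatment term and an error term, and nothing else. Women differ in hemoglobin, ferritin and the other outcomes before any treatment, and whatever part of that difference persists to month 3 stays in the error term. In a randomised comparison this causes no bias, and one value per woman needs no woman or month term. What is at stake is precision, which is scarce because the group size was set for convenience. Since the sample size is fixed, the choice of analysis is one of the few means left to improve precision.

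**Working it through.** **Inputs from the documents.** Five arms (3.3.6); 15 women per arm and 75 in total (3.3.5.2); significance level 0.05 (3.3.7.6). The stated total reproduces: 5 × 15 = 75. There is no power figure to reproduce.

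**Assumptions, not in the documents.** Two-sided test; one pairwise contrast of a treated arm with D0; true difference 0.8 SD; no dropout; common variance; one baseline slope shared by all arms; correlation r between pre-dose and month 3 values, varied from 0 to 0.7.

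**Unadjusted month 3 comparison.**
- Standard error = √(2/15) = 0.365 SD, with 75 − 5 = 70 residual df.
- Noncentrality = 0.8 / 0.365 = 2.19.
- Power = 58.0%. The difference detectable with 80% power is 1.04 SD.

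**ANCOVA on the pre-dose value.**
- One slope is estimated, leaving 69 df.
- Relative to the unadjusted comparison, the variance of the contrast is multiplied by (1 − r²)(1 + 1/68). The second factor, with 68 = 70 − 2, is the expected cost of chance baseline imbalance when the slope is estimated.

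| r | Variance factor | Power at 0.8 SD | Detectable at 80% power | Equivalent women per arm (15 / factor) |
|---|---|---|---|---|
| 0 | 1.015 | 57.3% | 1.05 SD | 14.8 |
| 0.3 | 0.923 | 61.3% | 1.00 SD | 16.2 |
| 0.5 | 0.761 | 69.7% | 0.91 SD | 19.7 |
| 0.7 | 0.518 | 85.2% | 0.75 SD | 29.0 |

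The loss at r = 0 is about 0.6 points (57.96% to 57.33% before rounding). Break-even is where (1 − r²)(1 + 1/68) = 1, at r of about 0.12. Simulation with common slopes agrees with these powers, with type I error close to 5% for both analyses.

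**Change from baseline is not a substitute.** Its variance factor is 2(1 − r). Power is 33%, 45%, 58% and 80% at r = 0, 0.3, 0.5 and 0.7. That is below ANCOVA at each of these values, and below the unadjusted comparison when r is under 0.5.

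**If slopes differ between arms.** With equal arms and equal baseline variance, the pooled slope b is about the mean of the arm slopes. An arm with slope β then has residual variance of about 1 + b² − 2bβ, in units where the outcome variance is 1.
- *Placebo 0.7, treated arms 0:* b = 0.7/5 = 0.14. D0 gives 1 + 0.0196 − 0.196 = 0.824 and D1 gives 1.020. Their mean is 0.92, against 0.518 with a common r of 0.7. Simulated power is about 59%, against 58% unadjusted.
- *D0 and D1 at 0, the other three arms at 0.6 (contrived):* b = 1.8/5 = 0.36. D0 and D1 each give 1 + 0.13 = 1.13, while the model's pooled residual variance is about 1 − 0.36² = 0.87. The standard error is therefore too small, and simulated type I error for D1 against D0 is about 8%.

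**The case against.** The strongest reply is that the analysis criticised here is not in the plan. The CRD sentence may describe only unblocked allocation, and no one-way ANOVA, final-visit comparison or exclusion of covariates is written down. That stands: use of baseline is unspecified, not ruled out. A reader might infer that the sponsor chose an unadjusted analysis, or that leaving baseline out makes the comparison wrong or biased. The documents support neither. Still, the CRD is all that is named, its standard analysis has no covariate, and adjustment decided after the data are seen invites selective reporting.

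Second, the benefit rests on r, which the documents do not give. Selecting only anemic women may narrow the baseline range and lower r, and at r = 0.3 the gain is only about 3 points. This also stands, so a gain of 12 or 27 points cannot be claimed for this trial.

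Third, a reader might infer that adjustment costs almost nothing. That holds statistically only under a common slope, as the unequal-slope cases show. It holds in practice only if a pre-dose sample is already planned, which section 3.3.7 leaves open.

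Fourth, the powers are for one contrast at 5%, while four contrasts are proposed for each outcome. At an illustrative 1.25% level (0.05 / 4), power for 0.8 SD would be about 36% unadjusted and 48% at r = 0.5. Adjustment does not rescue a small trial. The primary outcome and the multiplicity rule are separate matters that it leaves open.

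**Conclusion.** The point holds as a conditional improvement in precision. The only analysis that the plan points to makes no use of baseline. It is valid and unbiased, but it may leave removable variation in the error term of a trial with 15 women per arm.

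For one contrast at 0.8 SD, with common variance and a common slope, adjustment costs about 0.6 points of power at worst (r = 0). It gains about 3 points at r = 0.3, 12 at 0.5 and 27 at 0.7. With unequal slopes the gain can shrink to about a point, and the small-loss bound does not hold in general. The worth of the change depends on an unknown r, on similar slopes across arms and on a pre-dose measurement of each outcome. Within those limits it is worth making.

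**What to change.** Keep the CRD sentence as the description of allocation, and keep the 0.05 level. Add to 3.3.7.6:

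> Each outcome at the end-of-treatment (month 3) visit will be compared between assigned arms by ANCOVA in SPSS, with arm and the pre-dose value of that outcome as covariate, and contrasts of D1 to D4 against D0. As a sensitivity analysis, the arm by baseline interaction will be examined or robust standard errors reported.

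State in 3.3.7 that the monthly samples include a pre-dose (month 0) sample analysed for the same outcomes.

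The cost is slightly more analysis work and one residual degree of freedom (70 to 69). Under a common slope, power falls by about 0.6 points if baseline proves uninformative. If no month 0 sample was already planned, add one blood sample per woman, 75 in all, with the assays for each outcome to be adjusted.
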